MDAnderson Cancer Center

Protocol Abstract Page

A Phase II Study of TKI258 (Dovitinib Lactate) as Salvage Therapy in Patients with Stage IV HER2-negative IBC and Local or Distant Relapse 2010-0296

Study Chairman:	[name]
Department:	Breast Medical Oncology
[contact]
Unit:	1354
Full Title:	A Phase II Study of TKI258 (Dovitinib Lactate) as Salvage Therapy in Patients with Stage IV HER2-negative IBC and Local or Distant Relapse
Protocol Phase:	Phase II
Version Status:	Terminated 06/08/2018
Version:	19
Document Status:	Final

Core Protocol Information

Abstract

Objectives:

Primary

To determine an overall response (complete response [CR], partial response [PR] or stable disease [SD]) of dovitinib in patients with HER2-normal, local or distant relapse of metastatic inflammatory breast cancer

Secondary

• To evaluate safety analysis measures in terms of type, frequency and severity of adverse event reactions reported according to CTCAE v4.0

Exploratory Biomarkers:

• To explore the predictive values of baseline FGFR-R1, and VEGF-R1, signaling in tumor tissue (primary tumor or metastasis) before and during treatment with dovitinib.

• To determine the effect of dovitinib on the presence of CTC and CTCs with epithelial and/or EMT gene expression in PB.

• To collect and archive biopsy tumor tissue, serum and plasma for later hypothesis generating

associations

Rationale: (Be as concise as possible)

Inflammatory breast carcinoma (IBC) is one of the most aggressive forms of primary breast carcinoma that accounts for 1-6% of all invasive breast tumors in the United States and Western Europe. IBC is distinguished from other types of breast cancer by clinical, pathologic and molecular features. Additional pathologic characteristics of IBC include high grade, negative hormone receptor status and overexpression of HER2 and E-cadherin; all of which are poor prognostic factors. Molecular features of IBC include mutation of the p53 suppressor gene, and an increased expression of proangiogenic factors (basic fibroblast growth factor [bFGF], vascular endothelial growth factor [VEGF], interleukin [IL]-6 and IL-8).

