As a secondary analysis we will evaluate safety by grading each adverse event (e.g., neutropenia, neurotoxicity, and CINV) according to CTCAE v4.0 and reporting the type, frequency and severity. In order to understand the relationship of FGF R1, FGF9, FGF, and VEGF-R1 signaling in serum and those in the tumor tissue (primary tumor or metastasis) with tumor growth, a correlation analysis of the expression levels of the biomarkers and tumor size will be conducted. For each biomarker, baseline expression level (EB) and post-treatment expression level (EP) will be determined by Immunohistochemistry (IHC). Pearson product-moment correlation coefficient measuring the linear relationship between the percent change in expression level, [EB-EP]/EB, and the percent change in tumor size as measured by CT scan will be reported along with the associated 95% confidence interval and the p-value for testing that the true linear correlation coefficient is non-zero. A linear model will be used to assess the joint impact of down regulation of FGFR-R1 and VEGF-R1 on tumor growth. The change in the number of circulating tumor cells (CTC) at baseline as compared to the number post-dovitinib will be investigated using a paired t-test. If the change in CTC is not normally distributed based on Shapiro-Wilk test, we will consider a robust non-parametric procedure such as the Wilcoxon Rank-Sum test.

Data Safety Monitoring Board / DSMB at MDACC:

Select the name of the data safety monitoring board (DSMB) monitoring this protocol: Not Applicable

Please explain: This is not a randomized and not blinded study.

Protocol Monitoring:

Does this protocol have a schedule for interim and final analysis?

Provide a summary or schedule of interim analysis.

We will conduct an interim analysis after the first 22 patients following Simon's 2 stage min-max design.

Protocol Monitoring Plan:

Adverse events will be assessed according to the CTCAE version 4.0. All study patients who have received any dose of dovitinib will be evaluable for safety. Unexpected adverse events including laboratory adverse events deemed clinically significant by the investigator will be graded and recorded.

The ongoing review of safety data will include review of clinical AEs and SAEs. The NCI-CTC version 4.0 will be used to grade all AEs. An AE is an undesirable medical occurrence (sign, symptom, or diagnosis) or worsening of a pre-existing medical condition (diabetes, congestive

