heart failure, rheumatoid arthritis) that occurs after initiation of investigational product whether or not considered to be investigational product related. A worsening of an existing medical condition is one that was present at baseline (e.g., cancer, diabetes, migraine headaches, gout) and became more severe, more frequent, or increased in duration during investigational product treatment.

Reporting Procedures for AEs (>/=2 non-hematological and >/=3 hematological AEs) occurring after informed consent signing observed by the investigator or reported by the subject (whether or not attributed to investigational product), will be documented to the medical record then entered into the case report form. Abnormal laboratory values should not be reported as AEs; however, any clinical consequences of the abnormality should be reported as AEs. Hospitalization for elective surgery or routine clinical procedures that are not the result of an AE (e.g., surgical insertion of central line) need not be considered AEs and should not be recorded as an AE. Disease progression should not be recorded as an AE. The Investigator is responsible for verifying and providing source documentation for all adverse events and assigning attribution for each event for all subjects enrolled on the trial.

All patients will be followed for safety 30 days (+/- 10 days) after the last dose of dovitinib, and every 3 months for duration of up to one year or until death, whichever occurs first for response, PFS and OS. Patients will be followed a minimum of every 3 months by clinic visit (at MD Anderson or a local physician), telephone or e-mail correspondence.

Intellectual Property:

1. Does this study include any agents, devices, or radioactive compound (or No drug) manufactured at MD Anderson Cancer Center or by a contract manufacturer?

Investigational New Drugs (IND):

Does this protocol require an IND? Yes

Who is the IND Holder/Regulatory Sponsor? MDA IND Number: Pending

Please "Compose" an Investigator's Brochure Cover Letter. For technical assistance, contact the PDOL Help Desk, [contact].

No

Investigational Device (IDE):

Does this study utilize an Investigational Device?

Sponsorship and Support Information:

Does the Study have a Sponsor, Supporter or Granting Agency? Yes

Sponsor Name: Novartis Support Type: Industry Funding

This Sponsor/Supporter/Granting Agency will receive data.

Radioactive Material:		

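### The safety analysis covers every adverse event at any grade, but the only case report form instruction carries a severity threshold; the two scopes need to be reconciled

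*Combined protocol and SAP*

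**What the plan says.** The secondary objective in the Abstract is "To evaluate safety analysis measures in terms of type, frequency and severity of adverse event reactions reported according to CTCAE v4.0". Statistical Considerations turns this into an analysis that will "evaluate safety by grading each adverse event (e.g., neutropenia, neurotoxicity, and CINV) according to CTCAE v4.0 and reporting the type, frequency and severity". Neither sets a minimum grade.

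The Protocol Monitoring Plan then makes several statements of different scope:

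- On grading: "The NCI-CTC version 4.0 will be used to grade all AEs".
- On recording: "Unexpected adverse events including laboratory adverse events deemed clinically significant by the investigator will be graded and recorded". No grade floor is given, and the place of recording is not named.
- On reporting: the sentence that begins "Reporting Procedures for AEs (>/=2 non-hematological and >/=3 hematological AEs" says that such events, whatever their attribution, "will be documented to the medical record then entered into the case report form". This is the only mention of the case report form in the document.
- On laboratory findings: "Abnormal laboratory values should not be reported as AEs; however, any clinical consequences of the abnormality should be reported as AEs".
- On source records: the investigator must verify and provide source documentation, and assign attribution, for all adverse events.

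The document does not say which statement defines the safety dataset. It does not restrict the secondary safety analysis to events above a threshold.

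**The concern.** The analysis describes one set of events and the data-entry instruction describes a smaller one. A safety table built from a form filled in according to the reporting sentence would hold higher-grade events, yet under Statistical Considerations it would be presented as covering each adverse event. Two kinds of error follow. The number of patients shown with a given toxicity would be too low, because those whose worst grade is below the threshold drop out. Among the events that remain, the severe proportion would be too high, because the mild ones have left the denominator. Persistent low-grade toxicity of an oral drug given five days in seven would be hard to see.

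This matters because safety is the only secondary objective, the study is a single arm of at most 33 patients, and the plan lists a data safety monitoring board as not applicable. Data staff who follow different sentences of the same section could also build different tables.

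**Working it through.** No figure in the plan depends on this point, so there is nothing of the plan's own to reproduce. The check is a comparison of the texts, followed by an illustration on assumed rates.

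**Step 1: combine the recording statements as generously as possible.** Read the sentence on unexpected events as an addition to the reporting sentence, and read the threshold as CTCAE grade.

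| Event | Below threshold (grade 1 non-hematological, grade 1-2 hematological) | At or above threshold |
|---|---|---|
| Unexpected | Recorded, though the sentence does not name the case report form | Case report form |
| Expected | No stated route to the case report form | Case report form |

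The lower left cell stays empty even on this reading. The analysis in Statistical Considerations needs all four cells.

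**Step 2: direction of the error if the threshold governs.** For an expected toxicity, let A be the number of patients affected at any grade, f the share of them whose worst grade is below the threshold, and S the number with grade 3 or higher. S lies wholly above either threshold.

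- Patients recorded = A × (1 − f), which is less than A whenever f > 0.
- True severe share = S / A. Recorded severe share = S / [A × (1 − f)]. The ratio of recorded to true is 1 / (1 − f), which exceeds 1 whenever f > 0.
- For expected hematological events the threshold is itself grade 3, so S = A × (1 − f) and the recorded severe share is 100% by construction.

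**Step 3: illustration.** Inputs: 33 patients (the maximum sample size in Statistical Considerations); any-grade incidence of 50% (assumed); f from 20% to 80% (assumed). Then A = 33 × 0.50 = 16.5, and the expected number recorded is 33 × 0.50 × (1 − f).

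| f (assumed) | Patients recorded, of 16.5 | Apparent frequency | Inflation of severe share, 1/(1 − f) |
|---|---|---|---|
| 20% | 13.2 | 40% | 1.25 |
| 40% | 9.9 | 30% | 1.67 |
| 60% | 6.6 | 20% | 2.5 |
| 80% | 3.3 | 10% | 5 |

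The documents give neither an incidence nor a grade distribution for any toxicity. The table shows how the error behaves, not how large it is in this trial.

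**The case against.** The strongest reply is that these sentences govern different steps: CTCAE for grading everything, source documentation for everything, and form entry for the higher grades. That is a coherent hierarchy, and threshold-based collection is a legitimate choice. The schedule of evaluations also lists adverse events from screening to 30 days after treatment with no grade floor. The reporting sentence itself is awkward, looks like a heading run into the text, and does not contain the word *grade*.

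Much of this stands. The threshold as such is not an error, and reading it as CTCAE grade is an inference, although the plan names no other scale that would give those numbers a meaning. What the reply does not answer is that the analysis was left unrestricted. Source records and a visit schedule do not put an event into the analysis dataset, and a threshold in a data-entry instruction has little purpose unless it leaves out what lies below it.

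Four stronger readings are tempting, and the documents do not support them:

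- A reader might infer three mutually exclusive rules, one confined to unexpected events, so that known toxicities would not be recorded at all. The sentence on unexpected events does not say *only*, and the reporting sentence sets no limit by expectedness.
- A reader might infer that low-grade toxicity certainly never reaches the database. Unexpected events are to be recorded without a grade floor, and all events need source documentation. What is captured is undetermined, not known to be lost.
- A reader might put a figure on missed low-grade neutropenia, since it is the analysis's first example. The rule against reporting abnormal laboratory values as adverse events confounds this: asymptomatic neutropenia might go unreported at any grade.
- A reader might treat the phase I dose-limiting toxicities in the Rationale as the list of expected events. They are not presented as such, and no reference safety list is given.

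**Conclusion.** The scope of adverse event recording conflicts with the scope of the secondary safety analysis. If the reporting threshold governs the case report form, expected grade 1 non-hematological and grade 1-2 hematological events would be missing. Any-grade frequencies would be understated and the severe share of recorded events overstated.

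This rests on two assumptions: that the threshold means CTCAE grade, and that it decides what is entered. Both are the natural reading, but neither is stated. The direction of the error follows from them whenever any affected patient has a worst grade below the threshold; its size cannot be determined from the documents. Nor do the documents support saying that the safety endpoint cannot be produced at all: a summary of threshold-grade events would still be possible, provided it is labelled as that. The primary response analysis is not affected.

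**What to change.** Give the secondary objective, the safety paragraph of Statistical Considerations and the Protocol Monitoring Plan one common scope, in one of two ways.

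1. **Widen collection.** State that adverse events of all CTCAE v4.0 grades, expected or unexpected, are entered in the case report form, and tabulate the worst grade per patient for each event type. This keeps the objective as written. It costs wording in the protocol and the form, plus modest extra data entry for at most 33 patients.
2. **Narrow the claim.** Keep the threshold, add the word *grade*, and restate the objective, the analysis and every safety table as covering grade 2 or higher non-hematological and grade 3 or higher hematological events, expected and unexpected, plus any other events recorded under the sentence on unexpected events. Make no any-grade frequency claim. This has no data cost but gives a narrower safety statement.

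Under either option, say whether the sentence on unexpected events adds to the reporting rule and where those events are recorded. The Abstract page marks this version as terminated. If data entry has closed, the second option is still available, so that reported tables state which events they contain.
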